9.5.1.1 Assessing Study Site Effect

The primary endpoint will be assessed for site effect.

This study is a multicenter study and planned to have approximately 50 sites to enroll and randomize 286 subjects. A single site may not have sufficient number of subjects to allow meaningful within-site analysis of treatment effects stratified by baseline BSA category; therefore, study sites effect will be assessed by pooling sites on geographic basis to help interpret the results.

In pooling sites for analysis, the minimum cell size of 5 randomized subjects per treatment arm (placebo arm or apremilast arm) per stratum of baseline BSA (%) category (< 10% or \geq 10%) will be used. The pooling strategy is described as follows: 1) Sites will be pooled within each region (USA/Canada or EU) according to their rank based on site-specific sample size, starting with the smallest sites; i.e., within a region, the smallest sites will first be pooled until the pooled site has a minimum cell size of 5 for each of the four cells. 2) The remaining un-pooled sites will then be pooled within the region with the smallest pooled site. 3) In the rare case that all site pooled together in a region does not satisfy the above condition (a minimum cell size of 5 for each of the four cells), all sites in the region will be pooled together with the smallest pooled site of the other region.

Sites will be pooled together as described above in order to assess the site effect and site by treatment interaction on the primary efficacy endpoint.

For the pooled sites, summary and analyses will be based on ITT analysis set using MI imputation for missing values. Study site effect will be assessed for the primary endpoint by stratifying the analysis based on pooled site in addition to the stratification factor at randomization and examining whether the treatment differences adjusted for both stratification factor and pooled site are consistent with those from the primary analysis.

In addition, the consistency of the treatment effect across individual study sites (or pooled sites) will be assessed by performing a subgroup-type analysis with respect to the endpoints, with individual study sites (or pooled sites) treated as subgroups. Listings of response rates will be provided by individual study site and by pooled site. The treatment difference for each of the individual study sites (or pooled sites) will be reviewed to determine the effect among the individual study sites (or pooled sites).

9.5.2 Analyses of Secondary Efficacy Endpoint(s)

The main analysis for the secondary efficacy endpoints will be based on the ITT analysis set. The two-sided p-values and two-sided 95% confidence intervals (CIs) will be reported for treatment difference between placebo arm and apremilast arm. Details for multiplicity adjustment are described in [Section 9.1.2](#).

9.5.2.1 Binary Variables

The binary variables for secondary endpoints include the following:

- Proportion of subjects achieving an overall sPGA score of clear (0) or almost clear (1) with at least a 2-point reduction from baseline at Week 16
- Proportion of subjects with at least a 4-point improvement in GPI-NRS item score within the GPSS for subjects with a baseline score of ≥ 4 at Week 16

For these binary endpoints, the treatment difference between apremilast arm and placebo arm will be compared using CMH (Cochran–Mantel–Haenszel) test adjusting for the stratification factor at randomization. The two-sided p-values from the CMH test, the adjusted treatment difference in proportion using the weighted average of the treatment differences across the strata with the CMH weights, along with the associated two-sided 95% CIs using a normal approximation to the weighted average will be provided. Missing values will be imputed using the similar MI method as the primary endpoint, with sensitivity analysis using the NRI method.

9.5.2.2 Continuous Variables

The continuous variables for secondary endpoints include the following:

- Change from baseline in affected BSA at Week 16
- Change from baseline in DLQI total score at Week 16
- Change from baseline in GPSS total score and individual items scores at Week 16

The continuous efficacy endpoints will be analyzed based on the ITT analysis set using a mixed-effect model for repeated measures (MMRM) as the primary method. The MMRM model will use the change from baseline as the response variable and include treatment group, visit time, treatment-by-time interaction, and stratification factor as fixed effects, and the baseline value as a covariate. An unstructured covariance matrix will be used to model the correlation among repeated measurements. The Kenward-Roger adjustment will be used with restricted maximum likelihood (REML) to make proper

statistical inference. Within-group least-squares (LS) means and the associated SEs and 2-sided 95% CIs, treatment difference in LS means and the associated SEs and 2-sided 95% CIs and 2-sided p-values will be derived from the MMRM model for Week 16 and other scheduled visits (Week 2, 4, 8, and 12, if applicable) in the model.

9.5.3 Analyses of Exploratory Efficacy Endpoint(s)

[REDACTED]

9.6 Safety Analyses

9.6.1 Analyses of Primary Safety Endpoint(s)

Safety will be assessed via descriptive statistics. Unless otherwise specified, all safety analyses described in this section will be performed for both the Placebo-controlled Phase and the Apremilast-exposure Period. The safety analyses for the Placebo-controlled Phase will be based on the safety population and presented by treatment group (placebo arm or apremilast arm), and the safety analyses for the Apremilast-exposure Period will be based on the apremilast subjects as treated population and

presented by treatment group (Placebo/30 mg BID, 30 mg BID as Initiated and 30 mg BID as Treated).

For the analyses of AEs and lab marked abnormalities, the following endpoints will also be summarized:

- Subject incidence: Subject incidence (i.e., percentage [%] used in a frequency summary) is defined as the number of subjects with the specific event divided by the number of subjects included in the analysis. Subjects with multiple occurrences of the specific event in the specific analysis period will be counted only once in the numerator.
- Exposure-adjusted incidence rate (EAIR) per 100 subject-years: The EAIR per 100 subject-years is defined as 100 times the number of subjects with the specific event divided by the total exposure time (in years) among subjects included in the analysis. Subjects with multiple occurrences of the specific event in the specific analysis period will be counted only once in the numerator. The exposure time for a subject without the specific event is the treatment duration, whereas the exposure time for a subject with the specific event is the treatment duration up to the start date (inclusive) of the first occurrence of the specific event. The total exposure time in years is calculated by dividing the sum of exposure time in days over all subjects included in the analysis by 365.25. The EAIR per 100 subject-years is interpreted as the expected number of subjects with at least one occurrence of the specific event per 100 subject-years of exposure to the IP.

AEs and lab marked abnormalities will be summarized by subject incidence and EAIR for the Placebo-controlled Phase (Weeks 0 to 16) and for the Apremilast-exposure Period. In addition, selected summaries for the Apremilast Extension Phase (Weeks 16 to 32) and the Observational Follow-up Phase (4 weeks) may be presented if deemed necessary.

Descriptive statistics will be provided for vital signs, weight, height and BMI, laboratory values (continuous measurements) by treatment and visit, including the end of treatment visits. The baseline value, value at the time point, and change from baseline will be summarized for subjects who have values at baseline and at the time point.

Shift tables, that is, tables that summarize the baseline categories (normal, abnormal) versus the category at the end of the respective periods or versus the worst post-

baseline category, include subjects who have values at baseline and at least one post-baseline value. Similarly, in frequency summaries of shifts from baseline at scheduled study weeks per protocol, only subjects who have values at baseline and at the time point will be included.

9.6.2 Adverse Events

The Medical Dictionary for Regulatory Activities (MedDRA) version 24.1 or higher will be used to code all events categorized as adverse events to a system organ class and a preferred term with SOCs presented in the standard international order and PTs within SOCs will be presented in descending order of subject incidence.

The subject incidence of adverse events will be summarized for all treatment-emergent adverse events, drug-related treatment-emergent adverse events, serious adverse events, adverse events leading to discontinuation of investigational product, fatal adverse events and adverse events of interest.

9.6.2.1 Overall Summary of TEAEs

An overall summary of the following TEAE categories will be provided for the Placebo-controlled Phase (Weeks 0 to 16) for subjects with:

- Any TEAE
- Any drug-related TEAE
- Any severe TEAE
- Any serious TEAE
- Any serious drug-related TEAE
- Any TEAE leading to drug interruption
- Any TEAE leading to drug withdrawal
- Any TEAE leading to death

In addition, for Apremilast Exposure Period overall summary of TEAEs will also be provided.

9.6.2.2 All TEAEs

All TEAEs will be summarized by SOC and PT as well as by PT only (in descending order of subject incidence for the Placebo-controlled Phase (Weeks 0 to 16) and the Apremilast-exposure Period.

New events of all TEAEs by exposure interval (≤ 1 , > 1 to ≤ 4 , > 4 to ≤ 8 , > 8 to ≤ 12 , and > 12 Weeks) will be summarized for the Placebo-controlled Phase. Each subject is counted once for either subject incidence or EAIR for each applicable specific TEAE in each exposure interval where an event started. The denominator of a subject incidence is the number of subjects with treatment duration exceeding the lower bound of the particular exposure interval, while the denominator of an EAIR is the sum of the exposure time during the exposure interval (up to the first event start date for subjects with at least one event starting in the interval) among the same number of subjects as in the denominator of the corresponding subject incidence.

In addition, new events of all TEAEs by exposure interval (≤ 1 , > 1 to ≤ 8 , > 8 to ≤ 16 , > 16 to ≤ 24 , > 24 to ≤ 32 , > 32 Weeks) will be summarized for the Apremilast-exposure Period.

All TEAEs will be summarized by age category (< 65 , ≥ 65 years), sex, race and, if deemed necessary, by prior/concomitant psoriasis medication usage or baseline disease characteristics.

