5.2.1 Treatment-emergent Adverse Event

An AE is a treatment-emergent AE (TEAE) if the AE start date is

- On or after the date of the first dose of IP and no later than 28 days after the last dose of IP for subjects who have completed study treatment or have discontinued early by the time of database cut, or
- On or after the date of the first dose of IP for subjects who are ongoing with study treatment at the time of database cut.

If the treatment-emergent status of an AE is unclear due to a missing/incomplete start date, it will always be considered treatment-emergent, unless shown otherwise by data. Date imputation rules for missing AE start dates are described in [section 8.3.2](#).

Adverse event started more than 28 days after the last dose of IP will not be considered as a treatment-emergent AE.

5.2.2 Treatment-emergent Adverse Event Leading to Drug Withdrawal, Drug Interruption, or Death, and Drug-related Treatment-emergent Adverse Event

A TEAE leading to drug withdrawal is a TEAE for which the investigator indicates that the action taken with respect to IP is withdrawn permanently. A TEAE leading to drug interruption is a TEAE for which the investigator indicates that the action taken with respect to IP is interrupted. A TEAE leading to death is a TEAE for which the outcome is

fatal. Relationship to IP is based on the investigator's causality judgment; that is, a drug-related AE is an AE indicated by the investigator to have a suspected relationship to IP.

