7.4.1 Analysis Phases

Per protocol specification, data summary and analysis will be provided for the following phases:

7.4.1.1 Placebo-controlled Phase – Weeks 0 to 16

This phase starts on the day of randomization (Week 0/Visit 2), and stops on either: (1) the day the first IP for the next phase is dispensed at Week 16/Visit 7; or (2) the day of the discontinuation visit if the subject discontinued prior to or at Week 16/Visit 7; or (3) the last known study day if the subject is lost to follow-up prior to Week 16/Visit 7 during the phase.

For safety analysis in subjects who continued treatment in Apremilast Extension Phase (Weeks 16 to 32), the phase stopped one day prior to the first dose date in Apremilast Extension Phase.

For analysis of adverse events, TEAEs in the phase including those with start date at the first IP dose date through either: (1) one day prior to the first IP dose date in Apremilast Extension Phase (Weeks 16 to 32); or (2) 28 days after the last IP dose date for subjects who discontinue after only receiving treatment in the Placebo-controlled Phase.

For safety analysis of visit-based data (ie, laboratory parameters, vital signs, etc), the post-baseline data in the phase including those with assessments dates after the first IP dose date (exclusive) and through either: (1) the first IP dose date (inclusive) in Apremilast Extension Phase (Weeks 16 to 32); or (2) the last visit date within 28 days of the last IP dose date (prior to the first Follow-up Visit) for subjects who discontinue after only receiving treatment in the Placebo-controlled Phase.

At the time of the Week 16 analysis, if the date of the first IP dose date in Apremilast Extension Phase is not available in data base and the subject has not discontinued, the first IP dispensing date will be used instead.

7.4.1.2 Apremilast Extension Phase – Weeks 16 to 32

This phase starts on the day after the first IP is dispensed for the phase at Week 16/Visit 7, and stops on either: (1) the day of Week 32/Visit 10; or (2) the day of the discontinuation visit if the subject discontinued prior to or at Week 32/Visit 10; or (3) the last known study day if the subject is lost to follow-up prior to Week 32/Visit 10 during the phase.

For safety analysis, the phase started at the first dose date in the phase and ended at the last dose date.

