7.4.2 Apremilast-exposure Period for Safety Analysis

This period starts on the date of either: (1) the first dose of IP following randomization (Week 0/Visit 2) for subjects who are treated with apremilast from Week 0; or (2) the first dose of IP from the IP dispensed at Week16/Visit 7 for subjects who were originally treated with placebo and are treated with apremilast at Week 16.

This period stops on either: (1) 28 days after the last IP dose date for subjects completed or discontinued treatment from the study; or (2) data cut-off date for ongoing subjects.

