8.3.5 Treatment Duration

Partially or completely missing last dose dates will be imputed in the ADaM dataset for treatment duration.

When partially missing last dose date is available, set last dose date to the maximum of [the earliest possible date given the non-missing field(s) of last dose date, the minimum of (the latest possible date given the non-missing field(s) of last dose date, last known date in database, first non-missing Early Termination (ET) visit date)]

When last dose date is completely missing, set last dose date to the minimum of (last known date in database, first non-missing Early Termination (ET) visit date)

Last known date in database is defined as maximum of (last visit date, lab, vital signs, AE start or end dates, concomitant medications start or end dates, concomitant procedure date, last dose date from 'Disposition- Treatment' page, treatment exposure start or end dates where doses were completely or partially taken, death date).

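### The adverse-event percentages by exposure interval can count subjects who have stopped treatment in the numerator but not in the denominator, which matters where planned treatment ends on an interval boundary

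*SAP*

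**What the plan says.** **Numerator.** SAP 9.6.2.2 counts each subject once "for each applicable specific TEAE in each exposure interval where an event started". SAP 5.2.1 makes an event treatment-emergent if it starts "On or after the date of the first dose of IP and no later than 28 days after the last dose of IP". The analysis periods follow this. The Apremilast-exposure Period (SAP 7.4.2) ends "28 days after the last IP dose date for subjects completed or discontinued treatment from the study". TEAEs of the Placebo-controlled Phase (SAP 7.4.1.1) run to "28 days after the last IP dose date for subjects who discontinue after only receiving treatment in the Placebo-controlled Phase". SAP 7.4.1.3 adds that TEAEs from the follow-up weeks are also reported under a treatment phase. Events after the last dose are therefore in these tables by design.

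**Denominator.** SAP 9.6.2.2: "The denominator of a subject incidence is the number of subjects with treatment duration exceeding the lower bound of the particular exposure interval". The sentence stands in the paragraph on the Placebo-controlled Phase. The next paragraph extends the same table to the Apremilast-exposure Period, with a last interval of > 32 Weeks, and gives no other rule.

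**Treatment duration.** The readable text gives no formula. SAP 8.3.5 ties it to the last dose: "Partially or completely missing last dose dates will be imputed in the ADaM dataset for treatment duration". Nothing adds the 28 days.

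**Planned end of treatment.** SAP 3.1 has dosing through Week 32. Table 4 in SAP Appendix A sets the Week 32 target at day 225, and the protocol's Table of Events allows ± 4 days.

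**The concern.** The two parts of the percentage follow different clocks. The numerator runs to 28 days after the last dose, while the denominator stops at the last dose. In most intervals few subjects stop near the lower bound and little is lost. In the > 32 Weeks interval the lower bound is day 224, one day before the planned last visit. Nearly every completer of the apremilast arm can enter the numerator through the 28-day tail, while a few days of visit timing decide who enters the denominator. Subjects who switch from placebo are planned for 16 weeks of apremilast, so they meet the same boundary at > 16 to ≤ 24 Weeks.

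The tables are there to show how new events are distributed over time on drug. In the boundary rows the percentage would reflect scheduling as well as the drug. SAP 9.6.2.4 also calls for drug-related TEAEs by exposure interval.

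**Working it through.** **The plan's own figure.** The SAP gives no number for these percentages. Its sample size serves only to scale the example, and it reproduces: 25% vs 10%, two-sided 0.05, chi-square without continuity correction, gives 114 evaluable per arm with power 85.1%; 114 / 0.8 = 142.5, so 143 per arm.

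**Assumptions not in the documents.**
- Duration is last dose day minus first dose day plus 1, with first dose on day 1.
- Exposure intervals are counted from the first apremilast dose.
- The 20% dropout stated for the sample size is carried to Week 32: 143 × 0.8 = 114.4 completers. This cancels from the > 32 Weeks ratios.
- Week 32 visits fall evenly on days 221 to 229, with the last dose on the visit day or the day before.

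**One subject.** Last dose on day 222, event on day 235. The event is within 28 days of the last dose (222 + 28 = 250) and after day 224, so it counts in > 32 Weeks. The duration of 222 does not exceed 224, so the subject is not in the denominator.

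**Size in > 32 Weeks.** Let s be the share of completers with duration above 224 days and q the proportion of completers with a new event after day 224. The table reports q / s, so the inflation is 1 / s, and the figure passes 100% when s < q.

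| Visit timing | s | Denominator of 114.4 | Inflation | An illustrative 10% shows as |
|---|---|---|---|---|
| Even over ± 4 days, last dose on visit day | 5/9 | 63.6 | 1.80 | 18.0% |
| Even over ± 4 days, last dose the day before | 4/9 | 50.8 | 2.25 | 22.5% |
| 90% dosed past day 224 | 0.9 | 103.0 | 1.11 | 11.1% |
| 70% dosed past day 224 | 0.7 | 80.1 | 1.43 | 14.3% |
| 30% dosed past day 224 | 0.3 | 34.3 | 3.33 | 33.3% |
| All visits on day 225, last dose that day | 1 | 114.4 | 1.00 | 10% |
| All visits on day 225, last dose the day before | 0 | 0 | undefined | undefined |

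**Other intervals.** Here I compare the days on which a counted event can start, over all subjects, with the same days for denominator subjects only.
- *Placebo/30 mg BID, > 16 to ≤ 24 Weeks* (lower bound 112 days). A subject with last dose on post-switch day d contributes d + 28 − 112 days. With d even over 108 to 116, denominator subjects (113 to 116) give 29 + 30 + 31 + 32 = 122 and the others (108 to 112) give 24 + 25 + 26 + 27 + 28 = 130, so 252 / 122 = 2.07. With d over 109 to 117, it is (155 + 106) / 155 = 1.68.
- *30 mg BID as Treated, same interval.* Adding 114.4 × 56 = 6,406 days from subjects started on apremilast dilutes this to 1.21 and 1.16.
- *Placebo-controlled Phase, > 12 Weeks* (lower bound 84 days), with 20% dropout even over 112 days. Per randomized subject, denominator subjects give 0.8 × 28 + (0.2 / 112) × 1,190 = 24.525 days. Earlier stoppers give (0.2 / 112) × 406 = 0.725. The ratio is 25.25 / 24.525 = 1.03.

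**The case against.** The strongest reply is that the SAP never says that stopped subjects belong in the numerator. SAP 9.6.1 defines subject incidence in the usual way, as subjects with the event over subjects in the analysis. In 9.6.2.2 the exposure-adjusted rate sums time over the same subjects as the percentage's denominator and speaks of those with an event as if they were among them. A programmer might therefore restrict the numerator. But neither passage does so, and the counting rule and the 28-day window are explicit. If the restriction were applied silently, events after day 224 in subjects with duration of 224 days or less would appear in no interval. Either reading needs a written rule.

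Three further objections stand:

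- A reader might infer that the > 32 Weeks percentage is simply doubled. The documents do not support that as a fact. It rests on an even spread of visits and a last-dose convention, and the table above shows how far other timings move it.
- A reader might also infer an artificial late rise in event frequency. That is not shown. The preceding interval is 56 days long against a tail of about 28. At a constant 10% per 28 days it would show 1 − 0.9² = 19%, about level with 18.0% to 22.5%.
- The second location depends on which columns are produced. SAP 9.6.1 lists Placebo/30 mg BID for this period, whereas SAP 7.5.1.3 lists only 30 mg BID as Treated, where the effect is about 1.2 times.

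**Conclusion.** The concern holds as a fault in a stated rule. Followed literally, SAP 9.6.2.2 gives percentages whose numerator is not contained in the denominator. It is material in two places: > 32 Weeks for subjects started on apremilast, and > 16 to ≤ 24 Weeks in the Placebo/30 mg BID column if that column is shown (about 1.7 to 2.1 times under the even-spread assumption). In the randomized comparison up to Week 16 it is negligible. The factor of 1.80 to 2.25 is an illustration under assumed visit timing, not a prediction, and neither a fixed doubling nor a spurious late rise should be claimed. Safety is summarized descriptively, and the efficacy tests and overall TEAE percentages do not use this rule. The correction is worth making because a boundary row can be badly wrong in a safety table and the repair is cheap.

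**What to change.** In SAP 9.6.2.2:

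1. Count in each interval only events that start on or before the last dose, among subjects in that interval's denominator.
2. Report TEAEs that start after the last dose and up to 28 days in a separate row, with all subjects who ended treatment as the denominator. Splitting by event timing keeps each event in one row only.
3. Merge > 24 to ≤ 32 Weeks and > 32 Weeks into an open-ended > 24 Weeks interval. Deleting > 32 Weeks outright would leave on-treatment events after day 224 with no row.
4. State the formula for treatment duration, since the denominator depends on it.

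The same counting rule should serve the drug-related and serious TEAE tables by interval. The cost is a few sentences, one more table row and a slightly different interval layout; no new data are needed. In a Placebo/30 mg BID column, > 16 to ≤ 24 Weeks would then be a true proportion, but it would rest on a few days of exposure per subject and should be read that way.
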